All concomitant medications will be recorded in the eCRF. Use of rescue medication will also be recorded in the daily Headache Diary and in between visits to the clinical site.

4.8 Non-pharmacologic Adjunctive Treatments

The following complementary and alternative prophylactic approaches to migraine are prohibited during the participation in this study (and as applicable, should be recorded as part of the subject's retrospective headache history):

This document is confidential. It contains proprietary information of Supernus[®] Pharmaceuticals, Inc. Any viewing or disclosure of such information that is not authorized in writing by the Sponsor is strictly prohibited. Such information may be used solely for the purpose of reviewing or performing this study.

- Acupuncture
- Manual therapies (chiropractic spinal manipulation, occipital nerve block, massage therapy, physical therapy)
- Herbal and nutritional supplement therapies for migraine prevention (butterbur, feverfew and St. John's Wort)
- Cognitive-behavioral therapy, biofeedback, hypnosis
- Neuromodulation devices

Certain behavioral approaches (e.g., trigger factor avoidance, adequate hydration, migraine prevention diet, stress reduction techniques, regular exercise, and sleep hygiene) are allowed as long as they have been practiced for at least 1 month prior to Screening and will be continued throughout the study. These will be captured in the eCRF.

Prohibited interventions must be discontinued at least 2 weeks prior to Prospective Baseline, and no new non-pharmacologic therapies may be initiated within 1 month prior to Screening or during the study.

4.8.1 Prohibited Medications

Subjects may not be on any prohibited medication as indicated in the Inclusion/Exclusion Criteria.

Subjects treated with the following prophylactic medications should discontinue the treatment 14 days prior to the Prospective Baseline Period: antipsychotics, antimanics, barbiturates, benzodiazepines amitriptyline, lithium, valproic acid, tricyclic antidepressants, AEDs, calcium channel blockers, sedatives, SSRIs, NSRIs, CGRP receptor antagonists, CBD oil, herbal preparations/supplements such as feverfew or St John's wort and/or any medications that could impair or decrease thinking and concentration. It is recommended to taper off antipsychotics, barbiturates, benzodiazepine, tricyclic antidepressants, lithium, amitriptyline, valproic acid, SSRIs and NSRIs as applicable. ([Appendix 10.10](#)).

Note: Subjects must refrain from using these medications throughout the duration of the study.

Non-stimulant ADHD medications (e.g., clonidine, atomoxetine, viloxazine and guanfacine) must be discontinued 14 days prior the Prospective Baseline Period ([Appendix 10.10](#)).

5 STUDY METHODS

5.1 Study Visits and Procedures

All subjects who are randomized and take at least one dose of SM will be followed according to the protocol regardless of the number of doses of SM taken, unless consent for follow-up is withdrawn. The Sponsor or the Sponsor's designee must be notified of all

deviations from protocol visits or procedures, and these procedures, if applicable, will be rescheduled or performed at the nearest possible time to the original schedule.

Subjects/caregivers will be instructed to call study personnel to report any abnormalities during the intervals in between study visits and to come to the study site if medical evaluation is needed and as the urgency of the situation indicates. For emergency and other unscheduled visits to a medical facility other than the study site, medical records will be obtained by the Investigator or qualified designee as source data for study follow-up.

[Table 2](#) shows the Schedule of Events and Assessments for the study. Deviations from study visit windows will be recorded in the eCRF but will not require separate notification to the Sponsor.

Study visits must be scheduled according to the Schedule of Events relative to the Randomization Visit (Visit 3). Visits must not be scheduled relative to the previous visit. Bi-weekly telephone contacts will occur between study visits at Days 14, 43, 71, 99, 127, and 148 (± 2 days).

Table 2 Schedule of Events and Assessments

Assessments	Pre-treatment Phase		Treatment Phase							Post-treatment Phase			
	Screening ^a	Prospective Baseline	Randomization	Titration			Maintenance				Taper (EOS) (ET)	Safety Follow up (by phone)	
Study Visit #	1	2	3	PC	4	PC	5*	PC	6,7	8	PC	9	
Day of Study Visit	-56	-28	1	14 ^b	29	43 ^b	57	71,99,127 ^b	85,113	141	148 ^b	162	169-183 ^l
Week of Study Visit	-8 to -5	-4 to -1	-		4		8		12,16	20		21-23	24 to 26
Study Visit Window	up to 4wks before V2	4wks before V3	+ 2 days		± 7 days		± 7 days		± 7 days	± 7 days		± 7 days	± 7 days
Informed consent/assent	X ^c												
Demographics	X												
Retrospective 3-months headache history	X												
Randomization			X										
Inclusion/exclusion criteria	X		X										
Medical, family & psychiatric histories	X												
Physical & neurological examinations	X ^d				X ^d				X ^d	X ^d		X ^d	
Visual Neurological Exam	X											X	
Placebo Training		X			X ^e				X [V6]				
ECG (12-lead)	X						X					X	
Vital signs	X ^e	X ^e	X ^e		X ^e		X ^e		X ^e	X ^e		X ^e	
Hematology/Chemistry/Urinalysis	X	X					X			X		X ^m	
Serum pregnancy test (FOCP only)	X												
Urine pregnancy test (FOCP only)		X	X		X		X		X	X		X	
Urine drug screen	X						X		X	X		X	

Assessments	Pre-treatment Phase		Treatment Phase								Post-treatment Phase		
	Screening ^a	Prospective Baseline	Random-ization	Titration				Maintenance			Taper (EOS) (ET)	Safety Follow up (by phone)	
Study Visit #	1	2	3	PC	4	PC	5*	PC	6,7	8	PC	9	
Day of Study Visit	-56	-28	1	14 ^b	29	43 ^b	57	71,99,127 ^b	85,113	141	148 ^b	162	169-183 ^l
Week of Study Visit	-8 to -5	-4 to -1	-		4		8		12,16	20		21-23	24 to 26
Study Visit Window	up to 4wks before V2	4wks before V3	+ 2 days		± 7 days		± 7 days		± 7 days	± 7 days		± 7 days	± 7 days
Eye Exam			X						X [V6]			X	
C-SSRS	X	X	X		X		X		X	X		X	
Concomitant medications	X ^f	X ^f	X ^f	X	X ^f	X	X ^f	X	X ^f	X ^f	X	X ^f	X ^f
Review Headache Diary		X ^g	X ^g		X ^g		X ^g		X ^g	X ^g			
PedMIDAS	X		X				X			X		X	
PedsQL 4.0			X				X			X		X	
Cognitive assessment			X				X		X	X		X	X
Dispense SM			X ^h		X		X		X	X ⁱ			
Biweekly Phone Calls				X		X		X		X	X		
AEs			X	X	X ^j	X	X ^j	X	X ^j	X ^j	X	X ^j	X ^j
SM return & adherence					X		X		X	X		X	
PK blood sampling										X ^k			
Dose reduction instruction				X		X		X			X		

AE = adverse event; C-SSRS = Columbia Suicide Severity Rating Scale; ECG = electrocardiogram; EOS = end of study; ET = early termination; FOCP = females of childbearing potential; PC = Phone Call
PedMIDAS = Pediatric Migraine Disability Assessment Questionnaire; PedsQL = Pediatric Quality of Life Inventory; PK = pharmacokinetics; SM = study medication V = Visit

* Visit 5 is end of titration and beginning of Maintenance Period of the Treatment Phase hence included within Section 5.1.5 for clarification.

- a. Subjects who had used TPM or any disallowed prophylactic migraine therapy must discontinue the treatment at least 2 weeks before the start of the Prospective Baseline Period, with an appropriate taper when applicable.
- b. Bi-weekly telephone contacts will occur between study visits, at Days 14, 43, 71, 99, 127, and 148 (± 2 days).
- c. Informed consent/assent to be obtained prior to performing any study procedures.
- d. Physical examination (excluding genitourinary system) includes height and weight and a special assessment for the occurrence of decreased sweating and elevation in body temperature above normal. Neurological examination includes evaluation for impaired reflexes, balance problems, muscle weakness, paresthesia/numbness and tingling, speech difficulties, mental confusion or excessive fatigue.
- e. Seated (5 min) pulse rate, blood pressure, temperature, and respiratory rate. The vital signs' readings, except prior to dosing, will be performed within approximately 10 minutes prior to scheduled blood draws, where applicable.
- f. Concomitant medication includes headache rescue medicine (also recorded in the Headache Diary).
- g. Headache Diary training will be provided at Visit 2.

- h. Subjects will start the first dose on the same day of Visit 3 at the clinical site, instructions for dose titration will be provided.
- i. Provide instructions for dose tapering at Visit 8.
- j. Any subject who experiences an AE (whether serious or non-serious) or has a clinically significant abnormal laboratory test value will be followed by the Investigator for up to 30 days after the EOS visit. These subjects will be treated and/or followed up until the symptoms or value(s) return to normal/baseline or acceptable levels, as determined by the Investigator.

l. Safety Follow Up (by Phone) is not a site visit and falls within a range of 1-3 weeks after Visit 9/ET Visit occurs.

m. Subjects who discontinue from the study earlier than the EOS visit (visit 9) should undergo all EOS procedures included in visit 9 during the ET visit.

Note: Besides the testing specified during the respective visits in the Table 2 above, repeat testing for clinical laboratory parameters, vital signs, and/or ECG may be permitted, at the discretion of the Investigator. However, these repeat testing will require justification from the site and agreement with the Medical Monitor and the Sponsor on a case-by-case basis prior to conducting the tests.

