Safety Follow-up Telephone Call (Weeks 24 to 26):

Safety follow-up over the telephone will take place 1 to 3 weeks after the EOS/early termination (ET) visit. During the telephone call, all concomitant medications, cognitive assessment and AEs will be evaluated and recorded. Any subject who experiences an AE (whether serious or non-serious) or has a clinically significant abnormal laboratory test value will be followed by the Investigator for up to 30 days after the EOS/ET visit. These subjects will be treated and/or followed up until the symptoms or laboratory values return to normal/baseline or acceptable levels, as determined by the Investigator.

Figure 1 Study Schematic

EOS = end of study; V = visit

- Dosing will be based on weight and is flexible. [REDACTED]. [REDACTED]. [REDACTED]. The total daily dose will not exceed 100 mg/day (or 4 × 25 mg capsules/day). In the event of tolerability problems during titration, the Investigator may reduce the dose by 25 mg/week after Week 3. During maintenance, up to one dose reduction will be allowed for safety and tolerability during this period. Additional dose titration related to body weight changes will be reviewed and approved by the Medical Monitor and the Sponsor on a case by case basis.
- Subjects will receive a follow-up telephone call 1 to 3 weeks following discontinuation of study medication (Visit 9/EOS or early termination).

This document is confidential. It contains proprietary information of Supernus® Pharmaceuticals, Inc. Any viewing or disclosure of such information that is not authorized in writing by the Sponsor is strictly prohibited. Such information may be used solely for the purpose of reviewing or performing this study.

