Note: Abnormal results on screening laboratory tests and/or ECG may be repeated once per test at the discretion of the Investigator.

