6.8 Clinical Measurements

6.8.1 Laboratory

All clinical laboratory tests will be performed by a central laboratory as specified in the reference binder.

Details for collecting, handling, and shipping samples (including shipment addresses) will be detailed in a separate clinical laboratory manual. The Schedule of Events and Assessments ([Table 2](#)) shows the time points at which blood and urine samples will be collected for clinical laboratory tests.

[Table 3](#) presents the clinical laboratory tests to be performed.

Table 3 Clinical Laboratory Tests

Category	Parameters
Hematology	Red blood cell count, hemoglobin, hematocrit, platelets count, and white blood cell count with differential
Serum Chemistry	Electrolytes: Na ⁺ , K ⁺ , phosphate, chloride, bicarbonate
	Liver function tests: alkaline phosphatase, aspartate aminotransferase, alanine aminotransferase, total bilirubin, direct bilirubin, gamma-glutamyl transpeptidase
	Renal function parameters: blood urea nitrogen, creatinine
	Other: glucose, Ca ²⁺ , albumin, total protein, ammonia

Category	Parameters
Urinalysis and urine pregnancy test (FOCP only)	Complete urinalysis with microscopic examination, human chorionic gonadotropin
Urine Drug Screen	Cocaine, amphetamines, barbiturates, benzodiazepines, cannabinoids, opioids, phencyclidine, propoxyphene, methadone and alcohol
Serum Pregnancy Test (FOCP only)	Human chorionic gonadotropin

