6.8.2 Vital Signs

Vital signs' measurements (e.g, BP, pulse rate, temperature, and RR) will be obtained at each visit. BP and pulse rate will be measured after the subject has been sitting for 5 minutes. Route of temperature may be oral or temporal, per clinical practice, but should remain consistent throughout the subject's participation. Vital signs may be taken at any other time, as deemed necessary by the Investigator.

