6.8.8 Electrocardiograms (ECGs)

A 12-lead ECG will be obtained as per the Schedule of Events and Assessments (Table 2). Additional ECGs may be performed at other times if deemed necessary by the Investigator.

The ECG will be recorded while the subject is resting in a supine position. The ECG will electronically measure the PR, QRS, QT, and QTc intervals, and HR. All ECG tracings will be reviewed within 24 hours by the Investigator or qualified Sub-Investigator. PR intervals will be determined for each of these ECGs from a single reading. Invalid measurements will be repeated. QTc will be reported as QTcF.

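### Repeat labs, vital signs and ECGs need prior Medical Monitor and Sponsor agreement with no safety exception, in conflict with 6.8.2 and 6.8.8 and in tension with the duty to follow abnormal labs

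*Protocol*

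**What the plan says.** The Note closing protocol Table 2 first leaves repeat laboratory tests, vital signs and ECGs to the Investigator's judgement. It then requires a justification from the site and "agreement with the Medical Monitor and the Sponsor on a case-by-case basis prior to conducting the tests". Section 5.1.4 states the same rule for Visits 4 through 9. Neither place exempts a recheck made for safety.

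Five other places bear on the same decision:

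- Table 2, footnote j: a subject with an AE or a clinically significant abnormal laboratory value is to be "treated and/or followed up until the symptoms or value(s) return to normal/baseline or acceptable levels, as determined by the Investigator". Section 3.1 says the same: "treated and/or followed up until the symptoms or laboratory values return to normal/baseline or acceptable levels".
- Section 6.8.1: for laboratory tests it only points to Table 2, which "shows the time points at which blood and urine samples will be collected for clinical laboratory tests". It gives no discretion for extra samples.
- Section 6.8.2: "Vital signs may be taken at any other time, as deemed necessary by the Investigator".
- Section 6.8.8: "Additional ECGs may be performed at other times if deemed necessary by the Investigator", and "Invalid measurements will be repeated".
- Section 3.3.3, closing Note: "Abnormal results on screening laboratory tests and/or ECG may be repeated once per test at the discretion of the Investigator".

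**The concern.** The protocol gives the Investigator responsibility for following an abnormal value and puts a two-party approval in front of the usual means of doing so. Whether a low bicarbonate, a raised ammonia or a low neutrophil count has recovered is ordinarily known only from another blood sample. In a child who stays on drug, that sample at the site has to wait for both the Medical Monitor and the Sponsor.

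For vital signs and ECGs the difficulty is different: two sets of instructions give different answers. A site working from Table 2 would seek agreement before an extra ECG, while a site working from 6.8.8 would simply do it. At stake are the timeliness of a safety recheck and consistent conduct across about 35 sites. The sample size and the primary analysis are not affected.

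**Working it through.** The plan states no figure on this point to reproduce. The check is a comparison of texts, followed by schedule arithmetic.

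**1. Who decides on an extra measurement**

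| Test | Table 2 Note and 5.1.4 | Section specific to the test | Result |
|---|---|---|---|
| Vital signs | Prior agreement of both parties | 6.8.2: Investigator alone | Conflict |
| ECG | Prior agreement of both parties | 6.8.8: Investigator alone; invalid readings are repeated | Conflict |
| Labs on treatment | Prior agreement of both parties | 6.8.1: refers back to Table 2, no discretion | Nothing relieves the rule |
| Screening labs and ECG | Table 2 includes Visit 1, so its Note reaches them; 5.1.4 does not | 3.3.3 Note: one repeat per test, Investigator's discretion | Overlap |

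**2. Footnote j against the Note, for labs.** Footnote j sets a duty (follow the value) and an endpoint (normal, baseline or acceptable, as the Investigator judges). It does not order a repeat sample, set an interval or waive the Note. Both provisions can be obeyed together, provided agreement arrives. That is a tension, not a contradiction.

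**3. The period the rule governs.** Inputs: the laboratory row of protocol Table 2, which after first dose has entries at Days 57, 141 and 162, each with a window of ±7 days. Section 3.1 confirms that labs in Visits 6 to 8 are done at Visit 8 only.

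- Day 57 to Day 141: 141 − 57 = 84 days. Shortest: (141 − 7) − (57 + 7) = 134 − 64 = 70. Longest: (141 + 7) − (57 − 7) = 148 − 50 = 98.
- Day 141 to Day 162: 162 − 141 = 21 days. Shortest: (162 − 7) − (141 + 7) = 155 − 148 = 7. Longest: (162 + 7) − (141 − 7) = 169 − 134 = 35.

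**4. The tests it governs.** Section 6.6.9 lists 11 AESI entries. Four rest on laboratory values: metabolic acidosis (bicarbonate); hyperammonemia; raised alkaline phosphatase, creatinine or eosinophils; low white cells or neutrophils. 4/11 = 36%. Hyperthermia is not counted, because temperature is a vital sign under 6.8.2.

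**5. What these figures do not show.** They locate the rule in time and by test. They do not measure a delay. That would need the turnaround time for agreement, which the documents do not give.

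**6. A comparison inside the protocol.** Section 4.7 requires consultation with the Medical Monitor before treatment of AEs other than minor ones, but exempts acute conditions treated in an emergency room, hospital or office visit. Repeat testing has no matching exemption.

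**The case against.** The case for leaving the text alone has several parts.

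- **Section 8.2** says its requirements should not stop immediate action for subject safety, and asks only for prompt notice when an Investigator finds an urgent protocol change necessary. It concerns changes to the protocol, not the testing rule. It is an indirect fallback and does not remove the prior agreement.
- **The child is not unobserved between Days 57 and 141.** There are clinic visits at Days 85 and 113 with physical and neurological examination and vital signs, and calls at Days 71, 99 and 127. Section 5.1 tells caregivers to come to the site if medical evaluation is needed, and foresees care at other facilities. A child who stops drug has labs at the early termination visit (footnote m). All of this lessens the risk. None of it frees a site blood sample, in a child who stays on drug, from prior agreement.
- **A laboratory AESI already reaches the Sponsor within 24 hours** (6.6.9), so contact happens anyway. This makes quick agreement plausible, but reporting an event is not agreement to a test.
- **The conflicts can be read away.** Retaking an invalid ECG may count as completing the scheduled test, and 6.8.2, 6.8.8 and the 3.3.3 Note may be taken as specific rules that override a general one. These readings are reasonable, but the protocol does not say which text prevails, and additional ECGs and vital signs remain caught between two instructions.
- **Central control of off-schedule testing was added deliberately in Version 4.0.** That supports keeping it for non-safety repeats.

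A reader might infer more: that rechecks are forbidden, that a child goes unmonitored for 84 days, or that footnote j flatly contradicts the Note. The documents support none of these. Repeats are allowed with agreement, monitoring other than labs continues, and footnote j orders no repeat sample.

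**Conclusion.** The point holds as a low-priority but worthwhile correction. The prior-agreement rule has no safety exception. It conflicts with 6.8.2 and 6.8.8 for vital signs and ECGs. For labs, it places an approval between the Investigator's follow-up duty and a site recheck during the 84 days (70 to 98 with windows) between the two scheduled on-treatment labs. Four of the 11 AESI entries are of the laboratory kind.

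No harm or delay is demonstrated. With same-day agreement the practical effect would be small; with slow agreement it would be larger. The documents do not let one choose between these.

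The day counts rest on the protocol's schedule. SAP section 9.2 describes labs at every Treatment Phase visit, but the protocol's visit lists have none at Visits 4, 6 and 7. If the SAP description were the true one, the nominal interval after Day 57 would be 85 − 57 = 28 days. The missing safety exception and the conflict with 6.8.2 and 6.8.8 would be unchanged.

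**What to change.** Add to the Table 2 Note and to section 5.1.4:

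> Laboratory repeats made for safety (follow-up of an AE or AESI, or of a clinically significant abnormal value) may be done at the Investigator's discretion without prior agreement; the Medical Monitor is informed promptly afterwards. Additional vital signs and ECGs are governed by 6.8.2 and 6.8.8, and screening repeats by the Note in 3.3.3; these sections prevail and need no prior agreement. Prior agreement applies to all other repeats.

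Notice is limited to safety repeat labs. Extending it to every extra ECG or vital sign would add a burden that 6.8.2 and 6.8.8 do not impose, and would create a new mismatch with them.

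Cost: three sentences in two places, best carried in the next amendment, since section 8.2 sends changes affecting subject safety to the IRB. The Sponsor gives up prior approval of safety repeat labs and learns of them promptly afterwards. Sites send one short notice per safety repeat.

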5.1.1 Visit 1 – Screening (Day -56)

All reasons for screening failure will be recorded. If the subject passes screening but fails eligibility at Randomization visit (Visit 3), the reason(s) will also be recorded in the eCRF.

For subjects eligible for study participation, a Prospective Baseline Visit will be scheduled allowing for at least a 2-week/14-day washout of any disallowed migraine preventative medications the subject was receiving at Screening.

The following assessments will be conducted at this visit (screening assessments may be performed over multiple days):

- Obtain written informed consent/assent
- Obtain demographics
- Collect retrospective headache history, including non-pharmacological adjunctive treatments (last 3 months)
- Review inclusion/exclusion criteria
- Collect medical, family and psychiatric histories
- Perform physical examination (excluding genitourinary system) including height, weight and neurological examination
- Perform visual neurological exam
- Perform 12-lead ECG
- Record vital signs (pulse rate, blood pressure [BP], temperature, and respiration rate [RR])
- Collect blood samples for hematology and serum chemistry
- Collect serum sample for pregnancy testing (FOCP only)
- Collect urine sample for drug screen and urinalysis
- Administer C-SSRS
- Administer PedMIDAS scale
- Record concomitant medications

